The commercial supply of study medication will be provided by Insys Therapeutics Ltd. FSS was FDA approved in 2012 for “For the management of breakthrough pain in adult cancer patients who are already receiving and who are tolerant to around-the-clock opioid therapy for their underlying persistent cancer pain.” This study consists of two stages:

Stage 1. In-hospital pain management. Once patients are enrolled, our research nurse will be notified to provide careful instructions on medication use. Patients will be monitored for 3 episodes of breakthrough pain (Figure 1).

(1) First episode – patients will be given a single dose of breakthrough opioid from their existing PCA pump that is equivalent to 10% of their MEDD. The dose used in this study is consistent with our routine clinical practice. Immediately upon patient enrollment, the study physician will be notified and will determine the morphine equivalent daily dose (MEDD) in real time using standardized

equianalgesic ratios. We will then determine the doses of intravenous opioid needed (i.e. 10% of MEDD as per standard of care). For example, a patient had a MEDD of 200 mg/day at the time of enrollment. The IV opioid dose will be morphine 8mg IV x1 dose (or equivalent).

(2) Second episode

- a. The patient will be given a single dose of FSS that is equivalent to 16-32% of their MEDD (Table 2). Because FSS is available in fixed dosage forms, the actual % of MEDD will be determined. Pain intensity will be assessed at 30 minutes. A breakthrough pain intensity reduction of $\geq 2/10$, $\geq 33\%$ of baseline pain intensity, reduction of pain intensity to personal pain goal (PPG) score or below, OR absolute value below background pain level will be considered as an effective dose.
- b. If breakthrough pain not effective at 30 minutes, the patient will repeat the same dose one more time (with a cap of 1600 mcg total; i.e. dose given 30 minutes ago + dose now = 1600 mcg maximum), and their pain intensity will be reassessed over the next 30 minutes again.

(3) Third episode (at least 4 hours after second episode)

- a. If the patient required 2 breakthrough FSS doses for the last episode of breakthrough pain, or if the effective dose has not been identified, he/she will double the last administered dose, and pain intensity will be assessed at 30 minutes.

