- b. If breakthrough pain not effective at 30 minutes, the patient will repeat the same dose one more time (with a cap of 1600 mcg total; i.e. dose given 30 minutes ago + dose now = 1600 mcg maximum), and their pain intensity will be reassessed over the next 30 minutes again.

(4) The study assessments will be conducted Monday to Friday between 8AM and 4PM in the institution while under the supervision of our research nurse. Outside of this window, patients will need to use regularly prescribed breakthrough medications.

(5) While we expect a majority of patients will be able to identify an effective dose within the first 2 episodes of breakthrough pain, some patients may be discharged or their opioid infusion may be discontinued before an effective dose is identified. If that is the case, then their data will be censored for the primary objective.

(6) Once the effective dose is found, the first stage of this study is complete and they will no longer be on FSS. Patients who have identified an effective FSS dose may proceed to the next stage of this study upon discharge.

(7) We are limiting the total number of episodes to minimize attrition, minimize variability in basal opioid doses, and also because we are using an accelerated titration process so many patients will be starting already at higher doses than in the outpatient setting.

Table 2. FSS Dose for Breakthrough Pain Episode Based on Morphine Equivalent

Daily Dose

Morphine equivalent daily dose (mg)	FSS (mcg) starting dose	FSS starting dose % equivalent of MEDD	Titration schedule while in hospital (if effective dose already identified, there will be no need to titrate upwards)
70-109	100	16.1-25.0%	100/100 – 200/200
110-219	200	16.0-31.8%	200/200 – 400/400
220-289	300	18.2-23.9%	300/300 – 600/600
290-379	400	18.5-24.1%	400/400 – 800/800
380-469	500	18.7-23.0%	500/500 – 1000/600
470-579	600	18.1-22.3%	600/600 – 1200/400
580-669	700	18.3-21.1%	700/700 – 1400/200
670-750	800	18.7-20.9%	800/800 – 1600/NA

For intravenous opioid, the medication will be given by the research nurse or bedside nurse via the infusion pump. FSS will be provided by Dispensing Pharmacy. After providing careful instructions, the research nurse will keep the spray with the patient for ease of administration.

The following instructions will be given to the patient:

1. Swallow any saliva in your mouth.
2. Hold the medication spray unit upright using your index and middle fingers and thumb.

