Stage I. The use of opioids will be recorded during the study, and may be adjusted by the clinical team as per standard of care. If patients required an opioid rotation, they will not be able to continue with stage I of the study. If patients had breakthrough pain but were not able to use FSS (e.g. between 4 hour wait period or outside of study period in which research nurses are not available), they may continue with standard of care with intravenous opioids for breakthrough pain.

Stage II. Patients will be discharged on long and short acting oral opioids. They will be asked to use FSS as first choice for breakthrough pain (up to q4h PRN, maximum 4x/day). If they had significant pain not controlled by FSS, they will be asked to use their oral medication with at least 2 h since the last FSS dose. The use of long/short acting opioids will be titrated by the clinical supportive care team.

C.6. Research staff. An orientation will be held with research staff involved in this study to introduce them with the study design and to standardize the provision of each intervention.

C.7. Stopping rules. Patient may drop out of stage I if (1) after one time FSS dose reached 1600 mcg and effective dose not yet identified, (2) discharge, (3) death, (4) no longer on opioid infusion, (5) opioid rotation required, or (6) patient wish. Treatment will be stopped or adjusted based on the patient's vital signs. If the respiratory rate is 8 or less or if oxygen saturation is less than 90% for 2 minutes, the patient will be placed on oxygen (2 liters per minute) and our service will be notified.

Patients will drop out of stage II if (1) death, (2) no longer on opioid, or (3) patient wish.

C.8. Study assessments (Tables 3 and 4).

Table 3. Summary of Study Assessments during Stage 1

	Baseline	BTP1 (IV opioid)	BTP2 (FSS)	BTP3 (FSS if needed) ¹⁰
Demographics and baseline symptoms ¹	✓	-	-	-
Alberta Breakthrough Pain Assessment tool ²	✓			
Pain assessment ³	✓	0, 15m, 30m	0, 15 m, 30 m, 45 m ⁹ , 60 m ⁹	0, 15 m, 30 m, 45 m ⁹ , 60 m ⁹
Neurocognitive testing and vital signs ⁴	✓	30m	30 m, 60 m ⁹	30m, 60 m ⁹
Opioid use ⁵	-	-	✓	✓
Use of other pain medications ⁶	✓	✓	✓	✓
Acute adverse effects ⁷	✓	✓	✓	✓
Overall preference and global impression ⁸				End of stage I

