¹ patient initials, medical record number, date of birth, sex, race, education, marital status, cancer diagnosis, co-morbidities, ECSCP, CAGE questionnaire, Edmonton Symptom Assessment Scale (ESAS), personalized pain score. The study staff will retrieve the information from clinic station, and ask the patient for clarification if needed. ESAS is a validated questionnaire that measures 10 common symptoms in the past 4 hours (pain, fatigue, nausea, depression, anxiety, drowsiness, shortness of breath, appetite, sleep, and feeling of well being) using numeric rating scales.³⁸

² ABPAT is a validated assessment tool for breakthrough pain in cancer. The initial validation study used a Delphi process. It consists of 15 questions with three having 2 items, resulting in a total of 18 questions. The questions include the following: relationship to baseline pain, last time experienced, frequency, peak intensity of the BTP (0=no pain, 10=worst possible pain) and on an ordinal scale from (1=mild, 2=moderate, 3=severe), location (body map), pain quality with specified descriptors, time from onset to peak intensity, time from onset to end of episode, cause of BTP (triggers), predictability, general relief, relief from BTP medication, satisfaction with BTP medication, onset of pain relief, and satisfaction with onset of pain relief.

³ a 0-10 numeric rating scale that assesses pain intensity now, where 0= no pain at all, and 10=worst possible.

⁴ neurocognitive testing will be conducted using finger tapping, arithmetic, reverse memory of digits, and visual memory. We will also be monitoring vitals including heart rate, respiratory rate and blood pressure and O2 saturation.

⁵ all opioid use (name, dose, frequency, and use of breakthroughs) during the study, including the need for any dose escalation/reduction, will be recorded. The effective FSS dose will be recorded

⁶ use of other pain medications such as acetaminophen, NSAIDs, steroids will also be documented

⁷ acute adverse effects related to the use of opioids, such as dizziness, drowsiness, nausea, vomiting, anxiety itching/sneezing, and taste disturbance will be assessed using a numeric rating scale from 0-10 to assess the intensity "now".

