⁸ Patient global impression will be documented by the question "after starting your new treatment, how are your symptoms (i.e. pain)?" This has been used in multiple previous studies to assess patient perceived change.[11, 12] We will also ask patients which treatment (intravenous/spray/don't know) they prefer.

⁹ if a repeat FSS dose is needed

¹⁰ Breakthrough pain episode #3 will only be assessed if the patient did not achieve an effective dose after the first FSS dose

Table 4. Summary of Study Assessments during Stage 2

	Days 1-28 post discharge
Average pain intensity over last 24 hours ¹	Daily
Use of FSS ²	Daily
Pain medication and doses ³	Daily
Adverse effects ⁴	Daily
Complications ⁵	As they occur
Karnofsky Performance status ⁶	Weekly
Ease of use and perceived effectiveness ⁷	Weekly
Satisfaction with breakthrough opioid use ⁸	Weekly
Study satisfaction ⁹	End of study once

¹ a 0-10 numeric rating scale that assesses average pain intensity over the past 24 hours, where 0= no pain at all, and 10=worst possible.

² The number of BTP episodes and doses of FSS used per day will be documented. The duration of BTP episodes will also be recorded.

³ all opioid use (name, dose, frequency, and use of breakthroughs) during this stage, including the need for any dose escalation/reduction, will be recorded. Use of other pain medications such as acetaminophen, NSAIDs, steroids will also be documented.

⁴ adverse effects related to the use of opioids, such as dizziness, drowsiness, nausea, vomiting, anxiety, itching/sneezing, taste disturbance and constipation will be assessed using a numeric rating scale from 0-10 to assess the average intensity of last 24 hours.

⁵ the dates and reasons for acute complications such as re-admission, emergency room visits and falls will be recorded as they occur

⁶ an 11-point assessment scale that rates patients' functional status between 0% (death) and 100% (completely asymptomatic) based on their ambulation, activity level, and disease severity³⁷. A patient self-rated version will be used.

⁷ Ease of use and perceived effectiveness will be assessed using a 0-10 numeric rating scale

⁸ Satisfaction with breakthrough opioid use will be assessed by asking "How satisfied were you with the sublingual spray medication, taking the side effects, logistics and pain control into account? 0-10".

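### In FSS episodes, vital signs are scheduled only 30 minutes after each dose, so a respiratory event covered by C.7 may be acted on up to 30 minutes late, or may resolve unseen before the dose is repeated

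*Combined protocol and SAP*

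**What the plan says.** - **C.7 (Stopping rules)** states: "Treatment will be stopped or adjusted based on the patient's vital signs". Oxygen at 2 liters per minute and a call to the service follow "If the respiratory rate is 8 or less or if oxygen saturation is less than 90% for 2 minutes".
- **C.8, Table 3**, in the row "Neurocognitive testing and vital signs", lists 30 m for both FSS episodes (BTP2 and BTP3). It also lists 60 m, but footnote 9 limits that to "if a repeat FSS dose is needed".
- **The pain row of Table 3** is denser: 0, 15 and 30 m, then 45 and 60 m after a repeat.
- **Footnote 4 to Table 3** names the measurements, "We will also be monitoring vitals including heart rate, respiratory rate and blood pressure and O2 saturation", and gives no further times.
- **C.4, Stage 1, second and third episodes, item (b)**, sets the repeat rule: "If breakthrough pain not effective at 30 minutes, the patient will repeat the same dose one more time". The only stated limit is the cap, "dose given 30 minutes ago + dose now = 1600 mcg maximum".
- **C.4, Stage 1, item (4)** places the assessments in weekday working hours, "while under the supervision of our research nurse".

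**The concern.** C.7 can act only on what is observed. Between an FSS dose and the 30 m reading, the plan schedules no respiratory rate and no saturation, although a pain score is taken at 15 m. Two consequences follow.

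- An event that meets the C.7 criterion early and persists may wait until the 30 m reading before oxygen is given and the service is called.
- An event that begins and ends before 30 m may leave no trace in the only reading scheduled before the repeat. The same dose may then be given again on the pain score alone.

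The setting gives this weight. Patients are on a continuous opioid infusion, the titration is deliberately accelerated, and C.4 item (7) notes that many will start at higher doses than outpatients do. The Background also says that earlier FSS studies were all ambulatory. What is at stake is patient safety, not an endpoint or the precision of the dose estimate.

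**Working it through.** The plan states no figure for monitoring intervals, so there is none to reproduce. The inputs are the Table 3 times and the Table 2 doses.

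**1. Scheduled gap after each FSS dose**

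| Dose | Vital signs now | Longest gap now | With 15 m and 45 m added | Longest gap then |
|---|---|---|---|---|
| First dose, at 0 m | 30 m | 30 − 0 = 30 min | 15 m, 30 m | 15 min |
| Repeat, at 30 m | 60 m | 60 − 30 = 30 min | 45 m, 60 m | 15 min |

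**2. Repeat-dose decisions affected (Table 2)**

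All 8 MEDD rows allow a repeat in BTP2. In BTP3 the 670-750 mg row is 1600/NA, which leaves 7. The total is 8 + 7 = 15 repeat-dose points. Each now has one scheduled vital-sign reading since the previous dose; each would have two.

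**3. Episode totals when the dose is repeated (mcg, Table 2 rows in order)**

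- BTP2: 200, 400, 600, 800, 1000, 1200, 1400, 1600.
- BTP3: 400, 800, 1200, 1600, then 1000 + 600 = 1600, 1200 + 400 = 1600 and 1400 + 200 = 1600. The last row is a single 1600 dose.

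**4. Workload of the added readings**

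There is one extra reading per FSS dose. A patient whose first dose is effective has 1. The maximum is 4, or 3 in the 670-750 mg row. If all 30 patients receive FSS, the range is 1 × 30 = 30 to 4 × 30 = 120. The upper end assumes that every patient needs all four doses and none is in the 670-750 mg row.

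**5. Illustration only: is a short event present at a scheduled reading?**

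Assume that onset is uniform over the 30 minutes after a dose and that an event lasts D minutes. With gaps g between readings, the chance that it is present at a scheduled reading is the sum of min(D, g), divided by 30.

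| D (min) | Reading at 30 m only | Readings at 15 and 30 m |
|---|---|---|
| 2 | 2/30 = 7% | 4/30 = 13% |
| 5 | 5/30 = 17% | 10/30 = 33% |
| 10 | 10/30 = 33% | 20/30 = 67% |
| 15 | 15/30 = 50% | 30/30 = 100% |
| 20 | 20/30 = 67% | 30/30 = 100% |

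Under the same assumption, the mean wait from onset to the next scheduled reading falls from 30/2 = 15 min to 15/2 = 7.5 min. The documents support neither the uniform onset nor any value of D. The table shows the direction of the change, not a risk.

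**The case against.** The strongest reply is that Table 3 is a summary of assessments, not the whole monitoring plan. C.7 is not tied to its time points. Footnote 4 says that vital signs are monitored, C.11 promises careful monitoring throughout, and a research nurse supervises. A saturation criterion lasting 2 minutes suggests sustained observation. A patient too drowsy to answer at the 15 m pain contact could be noticed. All of this makes earlier detection possible, and the 30-minute delay is a bound on scheduled readings, not a prediction. But none of these passages sets a frequency, a device or a reading before 30 m, and a low respiratory rate or saturation can be missed if it is not measured.

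Second, the 30 m reading coincides with the repeat decision and C.7 governs treatment generally, so an event still present can be caught. That stands if vital signs are taken before the repeat, an order the text does not set. It does not help with an event that has ended, or shorten the wait for one that began early.

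Third, the risk is already limited: opioid-tolerant inpatients, starting doses scaled to MEDD, a cap per episode, at least 4 hours between FSS episodes, and IRB and DSMB oversight. These lower the risk but do not fill the gap.

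Fourth, 15 minutes is a choice of convenience and only a partial remedy. This stands. In the illustration, two thirds of 5-minute events would still fall between readings. One spot value does not establish a 2-minute desaturation, and nothing is added after the last check.

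**Conclusion.** The concern holds. Each FSS dose has one scheduled vital-sign reading, 30 minutes after it, and that is the only one scheduled before a possible repeat. The longest scheduled gap between a dose and the last check can be halved, from 30 to 15 minutes, at all 15 repeat-dose points in Table 2. Late or missed detection is a possibility that follows from the schedule, not a demonstrated harm. The documents give no rate, onset or duration for respiratory events, so no probability can be attached to it. The conclusion rests on reading Table 3 as the only stated timing for vital signs in these episodes, and no other section gives one. This is an inexpensive safety improvement that should be made.

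**What to change.** In the vital-sign row of Table 3, for BTP2 and BTP3, add respiratory rate and O2 saturation at the existing 15 m pain contact, and at 45 m when the dose is repeated. Leave the neurocognitive tests at their present times. Apply C.7 unchanged to the new readings.

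The cost is one table row and the matching case report form fields. The contacts and both measurements are already in the plan, so no staff or procedure is added. The burden is 1 to 4 brief readings per patient, usually fewer than 4 because titration stops at the effective dose.

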3. Point the nozzle into your mouth and under your tongue.
4. Squeeze your fingers and thumb together to spray the medication under your tongue.
5. Hold the medicine under your tongue for 30-60 seconds. Do not spit out any medicine. Do not rinse your mouth.
6. The spray unit will remain locked after use.

If a patient did not complete stage 1 on day 1, he/she will resume standard of care outside of study hours, and continue on where he/she left off with the next episode of breakthrough pain when the study resumes (i.e. Monday to Friday 8AM and 4PM).

Stage II. Out-of-hospital pain management. Upon completion of stage I, patients will revert back to their intravenous opioid regimen as prescribed by the Supportive Care team. Patients will be monitored and treated as per routine clinical practice. At the time of discharge, patients will be able to proceed to Stage II if they meet the following criteria:

- Must be willing to return to the Supportive Care Center within one to four weeks of discharge
- Discharged on a standard regimen of long acting and short acting opioid (non-FSS), with MEDD of at least 60 mg/day
- Effective FSS dose identified in Stage I

- The MEDD at time of discharge should be within 2 fold (i.e. 50% - 200%) of the MEDD at the time of effective dose.
- Willing to use FSS at home as their first choice for breakthrough pain for 4 weeks

During stage II, patients will be asked to use FSS (at effective dose) as their first choice of their rescue pain medication instead of oral opioid for breakthrough pain. FSS will be prescribed as q4h PRN for pain use to a maximum of 4x/day for up to 4 weeks. Patients will always have their regular short acting oral opioid as a backup every 2 hours PRN for breakthrough pain (but not given at the same time as FSS). For example, after FSS use if a patient still has pain, he will wait for at least 2 hours before using the short acting opioid. After at least another 2 hours if another episode of breakthrough pain occurred, he may use another dose of FSS for pain relief.

We will document the pattern of FSS use, its safety, and adverse effects in the outpatient setting. During this time, patients will have access to Supportive Care Service by telephone or in person 24/7. Furthermore, they will be able to discuss FSS use with our research team, with physicians available to discuss titration if needed.

C.5. Medication use during the study.

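### The Stage II exit rule in C.7 is looser than the opioid-tolerance conditions that justify home FSS, and no rule prompts an FSS review when scheduled opioid is stopped or cut below the entry limits

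*Combined protocol and SAP*

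**What the plan says.** Entry to Stage II (C.4, Stage II) is decided at discharge. Two of the criteria concern background opioid: "Discharged on a standard regimen of long acting and short acting opioid (non-FSS), with MEDD of at least 60 mg/day", and "The MEDD at time of discharge should be within 2 fold (i.e. 50% - 200%) of the MEDD at the time of effective dose".

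After entry, patients are asked to "use FSS (at effective dose) as their first choice of their rescue pain medication instead of oral opioid". The prescription is stated as "FSS will be prescribed as q4h PRN for pain use to a maximum of 4x/day for up to 4 weeks". C.4 also gives patients access to the research team, "with physicians available to discuss titration if needed".

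Background opioid need not stay where it was at discharge. C.5, under Stage II, says: "The use of long/short acting opioids will be titrated by the clinical supportive care team". It gives no lower limit.

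The exit list in C.7 reads: "Patients will drop out of stage II if (1) death, (2) no longer on opioid, or (3) patient wish". The preceding paragraph of C.7, on Stage I, contains "Treatment will be stopped or adjusted based on the patient's vital signs", followed by a respiratory-rate and saturation rule with oxygen.

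**The concern.** The protocol's case for giving FSS rests on tolerance to background opioid. The indication cited in C.4 is for patients on, and tolerant to, around-the-clock opioid. C.11 ties its expectation of no significant side effects to opioid-tolerant patients. The Stage II entry limits put numbers on the same premise.

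C.7 does not carry that premise past discharge. Exit (2) applies when the patient is off opioid. It does not clearly apply to a patient whose scheduled opioid has been stopped and who keeps only oral rescue. It does not apply to a patient whose scheduled dose has been cut below 60 mg/day, or below half the MEDD at which the FSS dose was found to be effective. Home FSS could then continue, at a dose chosen against a higher background, below the level the protocol required to start it.

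What is at stake is patient safety at home, and with it the safety and tolerability part of secondary objective #2.

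**Working it through.** **1. The texts side by side.**

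| Place | Background-opioid condition | When it applies |
|---|---|---|
| C.4, indication | On and tolerant to around-the-clock opioid | General premise |
| C.4, Stage II criteria | MEDD at least 60 mg/day; 50% to 200% of MEDD at effective dose | Once, at discharge |
| C.5, Stage II | Clinical team may titrate; no lower limit | Up to 4 weeks |
| C.7, Stage I exits | Off the infusion, or opioid rotation needed | Throughout Stage I |
| C.7, Stage II exits | Off opioid | Throughout Stage II |

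In Stage I a change of background opioid can itself end participation. Stage I gives at most 4 FSS doses, under nurse supervision and with vital signs (C.1, C.4, Table 3). Stage II allows up to 4 x 28 = 112 doses at home, and Table 4 schedules no vital signs. The stage with more unsupervised exposure has the weaker rule.

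**2. The plan's own figure.** Table 2 gives 100 mcg as 25.0% of a MEDD of 70 mg/day, so 100 mcg corresponds to 0.25 x 70 = 17.5 mg. At the top of that band, 17.5/109 = 16.1%, as the table states. The same ratio reproduces all eight rows.

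**3. Effect of a cut with FSS unchanged.** If MEDD falls by a fraction f, the dose as a share of MEDD is multiplied by 1/(1 - f):

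- f = 0.25: 1/0.75 = 1.33
- f = 0.50: 1/0.50 = 2.00

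This does not depend on the conversion ratio. As an example, take 100 mcg effective at 70 mg/day, starting from 25.0%. After a 25% cut it is 17.5/52.5 = 33.3%, and after a 50% cut 17.5/35 = 50.0%.

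**4. How large a cut crosses an entry limit.** Let E be the MEDD at the effective dose. The lower limit is max(60, 0.5E); the two parts are equal at E = 120. For a patient discharged at MEDD equal to E (an assumption), the cut that reaches the limit is 1 - max(60, 0.5E)/E:

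- E = 70: 1 - 60/70 = 14.3%
- E = 110: 1 - 60/110 = 45.5%
- E = 120 or more: 50%

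For a patient discharged exactly at a lower limit, any cut crosses it.

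**5. Sample size.** D.1 is based on the Stage I effective dose. Its half-widths reproduce (for example 1.96 x 10/sqrt(22) = 4.18, stated as 4.2%), and no Stage II exit enters them.

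**The case against.** The strongest reply is that Stage II is not unsupervised. Patients have 24-hour access to the service, and physicians can discuss titration (C.4). The research nurse calls at least twice a week, significant concerns go to the principal investigator, and diaries are checked every 2 weeks (C.8). Adverse effects are scored daily (Table 4), and the IRB and DSMB monitor the study (C.11). The team that would cut the background opioid is the supportive care team itself, not an outside prescriber unaware of FSS. All of this stands, and it is why the point is minor. It does not close the gap, because these safeguards respond to concerns, symptoms or requests. A planned cut in scheduled opioid need cause no complaint before the next spray, and nothing written makes anyone look at the FSS dose.

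Three stronger readings are tempting, and the documents do not support them.

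- *That C.7 prevents withdrawal for an adverse effect or on investigator judgement.* C.7 lists when patients leave Stage II. It does not bar a clinician from stopping FSS, so an added exit for these reasons would only write down what can already be done. Reasons for dropout are already captured (C.10, D.1).
- *That C.7 produces very large doses relative to MEDD.* A doubled dose of 400 mcg (70 mg by the Table 2 ratio) at a MEDD of 60 mg/day is 70/60 = 116.7%. The discharge criteria already permit that; the exit list does not cause it. Larger figures need several assumptions stacked together.
- *That the vital-sign rule covers home use.* The sentence is not expressly limited to Stage I. Its position, the oxygen instruction and the absence of vital signs from Table 4 make it an in-hospital rule.

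**Conclusion.** The point holds as a minor safety improvement. Exit (2) is looser than the protocol's own tolerance premise, and no rule requires FSS to be reviewed or stopped if scheduled opioid is stopped or falls below the entry limits.

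The size is a multiplier of 1.33 or 2.00 on each dose as a share of MEDD, for a 25% or 50% cut. It rests on the FSS dose being left unchanged, which the protocol allows but does not require. A 25% cut does not by itself breach a limit for every patient: a patient discharged at an unchanged MEDD of 120 mg/day or more would need a cut of more than 50%. The documents give no frequency for such cuts, so no expected number of affected patients can be stated, and no harm has been shown. A reader might infer that the secondary results are biased. Nothing here shows that: opioid doses, FSS use and adverse effects are recorded daily whatever the exit rule.

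**What to change.** Amend the Stage II part of C.7 in two places.

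(a) Change exit (2) to: *no longer on around-the-clock (scheduled) opioid*.

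(b) Add: when prescribed scheduled opioid is reduced so that MEDD, calculated in the same way as for Stage II entry, falls below 60 mg/day or below 50% of the MEDD at the effective dose, a physician promptly reviews the FSS dose and decides to continue, reduce or stop it. The research nurse checks for this at the planned calls, from the daily opioid record.

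Because (b) starts from a reduction in the scheduled prescription, a fall in oral rescue that comes only from using FSS instead does not trigger it. No separate rule for rescue doses is needed.

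The cost is a short amendment and a simple MEDD check when scheduled opioid is reduced. The doses are already recorded daily (Table 4, footnote 3), and at least 2 x 4 = 8 calls per patient are planned over 4 weeks. A few patients may reduce or leave FSS before day 28, which slightly shortens the Stage II use data.
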